Antagonist of the glucagon-like peptide 2 (GLP-2) receptor

*Department of Biomedical Sciences,
University of Copenhagen*

*H-24000668
Date: 06/01/25*

Title: Antagonist of the glucagon-like peptide 2 (GLP-2) receptor

Approved ethical committee ID: H-24000668

Project Group:

[name] [name], PhD (PI)

[name] [name], PhD-student

[name], B.A. Science

[name], Med.-student

[name], cand.scient.

[name] [name]

[name], cand. scient., PhD

[name], cand.scient. PhD

[name] [name], MD, DMSc

[name] Bo [name], DMSc

[name] [name], MD, PhD

Background:

Previous studies have shown that GLP-2 increase abdominal blood flow to the intestines. The studies that reveal this effect are built on results of exogenous distributed GLP-2 and have not investigated the endogenous effects of GLP-2. We have previously performed a single study in healthy males with the use of flow sensitive magnetic resonance imaging (MRI) where supraphysiological doses of GLP-2 injections greatly increased the blood flow in the superior mesenteric artery and portal vein but there were surprisingly no changes after intake of oral glucose. In this study we investigate if physiological doses of GLP-2 will increase the blood flow to the intestines and if different doses of the GLP-2 receptor antagonist (GLP-2(3-33)) can alter these flow changes in humans of both genders.

Aim: We aim to determine the right dose of the GLP-2-receptor antagonist to use in physiological research in healthy humans. We hope to be able to achieve the maximal blocking of the GLP-2 receptor possible and at the same time reduce expenses and infusion volume for the participants in future studies. We thereby hope to characterize the use of the GLP-2 receptor antagonist GLP-2(3-33) as an essential tool in research of the role of the human GLP-2 receptor in bone metabolism and nutrient uptake in the future.

Hypothesis: The hypothesis of this study is that the GLP-2(3-33) can block the effects of GLP-2 on the blood flow to the superior mesenteric artery and the portal vein.

Design:

Randomized, placebo controlled, crossover, single blind design in 10 healthy participants.

Baseline information:

A description of the baseline measured will be presented in a table, including the following measures: Age, Weight, Height, BMI, Hemoglobin, Leucocytes, Vitamin D, Fasting glucose, HbA1c, Sex, and Blood pressure. The data will be presented in Median and range.

Statistical analysis and graphs:

The flow data is analyzed in Rs studio by a linear mixed model, that pairs the data, and compared the interventions after steady state of the infusion of GLP-2(3-33) antagonist. The primary statistical analysis will be done between the interventions: Physiological dose of GLP-2 injection and highest dose of GLP-2-antagonist infusion + GLP-2 injection and placebo infusion. Furthermore, the data will be presented in GraphPad Prism 10. A data table will present the flow measurements of each intervention, including mean and 95% confidence intervals

Criteria:

[figure not shown]
Inclusion

- 1) Age 18-70 years
- 2) BMI 19-28 kg/m²

Exclusion

- 3) Chronic illness that affects the cardiovascular system or gastrointestinal tract
- 4) Treatment with medicine or supplements that cannot be paused for 12 hours
- 5) Intake of above 14 alcoholic drinks per week or substance abuse
- 6) Liver enzymes (ALAT) above 2 times normal values
- 7) Decreased kidney function (eGFR below 90 or creatinine levels over reference value)
- 8) Low blood percentage (hemoglobin below reference value)
- 9) Any condition or disease that the persons responsible for the study find would interfere with the participation of the study.

Methods and outcomes: Phase-contrast magnetic resonance imaging (PC-MRI) is used to calculate blood flow in the blood vessels: superior mesenteric artery, portal vein, celiac trunk and hepatic artery during the infusion of either saline or GLP-2(3-33) receptor antagonist and injection of GLP-2. The main outcome of the study is blood flow in superior mesenteric artery. On each study day, 8 MRI scans are performed (-32 min to 60 min after start of infusion) and four blood samples are taken. Blood glucose is measured bedside on whole blood. The blood samples collected are kept for analysis of GLP-2(1-33), GLP(3-33) and markers of bone metabolism.

Adverse event:

All adverse events (AEs) or serious adverse event (SAE) are reported throughout the whole study period, any adverse event reported will be informed to the ethical committee responsible for the study. All AEs including local and systemic reactions not meeting the criteria for SAEs will be captured on the appropriate case report form. Information to be collected includes event description, time of onset, qualified medical professional's assessment of severity, relationship to study product (assessed only by those with the training and authority to make a diagnosis), and time of resolution/stabilization of the event. All AEs occurring while on study must be documented appropriately regardless of relationship. All AEs will be followed to adequate resolution.

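### The main outcome is MRI flow, but nothing in the single-blind plan provides for measuring it without knowledge of the intervention

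*Combined protocol and SAP*

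**What the plan says.** The combined protocol and SAP deals with masking in one line, under Design: "Randomized, placebo controlled, crossover, single blind design in 10 healthy participants". It does not name the masked party.

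Under Hypothesis, the expected result has a direction: "The hypothesis of this study is that the GLP-2(3-33) can block the effects of GLP-2 on the blood flow" in the superior mesenteric artery and the portal vein. Under Background, the plan also asks "if different doses of the GLP-2 receptor antagonist (GLP-2(3-33)) can alter these flow changes".

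Under Methods and outcomes, "Phase-contrast magnetic resonance imaging (PC-MRI) is used to calculate blood flow in the blood vessels", four vessels are listed, and "The main outcome of the study is blood flow in superior mesenteric artery". The scan schedule is "On each study day, 8 MRI scans are performed (-32 min to 60 min after start of infusion".

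Under Statistical analysis and graphs, a linear mixed model on paired data "compared the interventions after steady state of the infusion of GLP-2(3-33) antagonist". The primary contrast is introduced as "The primary statistical analysis will be done between the interventions: Physiological dose of GLP-2 injection and highest dose of GLP-2-antagonist infusion". I read the full sentence as GLP-2 with the highest antagonist dose against GLP-2 with placebo infusion.

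**The concern.** Flow from phase-contrast MRI has to be calculated from images. The plan does not say whether a person outlines the vessel or software does, who decides that a scan is unusable, or whether those steps are taken without knowledge of the study day's infusion. If only the participant is masked, the person deriving the main outcome may know the intervention and the result the hypothesis predicts.

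A reading difference that tracks the intervention is not noise. It shifts the estimated effect of the antagonist, and could also distort the comparison between doses that is meant to guide dose choice in later studies. The crossover removes stable differences between participants, but not an error attached to the intervention.

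**Working it through.** **Search for a masking provision.** I read every section for coded or anonymised files, a masked or independent reader, automatic vessel outlining, a masked analyst, or a masked rule for excluding scans. None is present. The documents show neither that the reader is unmasked nor that outlining is manual; they leave both open.

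**Does the stated analysis remove a reading difference?** Let *pre* and *post* be true flow before the infusion and at steady state.
- Additive offset *a*, constant within a session: it cancels in absolute change, (post + a) − (pre + a) = post − pre.
- Proportional error *b*, constant within a session: it cancels in relative change, (1 + b)post / [(1 + b)pre] = post / pre.
- Neither cancels when post-infusion flow alone is compared, as post + a and (1 + b)post still carry the error.
- A difference confined to the later scans cancels in none of these.

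Scans start at −32 min, so pre-infusion scans appear to exist. The plan nevertheless states a comparison after steady state and mentions no change from baseline. As written, even a session-constant difference would stay in the contrast.

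**Size.** The plan has no figure to reproduce: it gives no alpha, power, expected effect or SD. The following only illustrates how a shift would act; none of the shifts is evidence about this trial. Assume a paired t-test with n = 10 at two-sided 5%, no true difference, and a reading shift of *s* SDs of the paired difference. The test statistic is then noncentral t with 9 degrees of freedom and noncentrality s × √10.

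| Assumed shift s | s × √10 | Type I error |
|---|---|---|
| 0 | 0 | 0.050 |
| 0.1 | 0.316 | 0.059 |
| 0.2 | 0.632 | 0.088 |
| 0.3 | 0.949 | 0.136 |
| 0.5 | 1.581 | 0.293 |

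**Workload of coding.** The number of interventions is not stated. Mention of different doses and of a highest dose implies at least 2 antagonist doses; with placebo infusion that is at least 3 interventions. One study day per intervention is assumed, as are 1 to 5 minutes per file.
- Sessions: 3 × 10 participants = 30.
- Scans: 30 × 8 = 240. Time: 240 × 1 min = 4 h; 240 × 5 min = 20 h.
- If each vessel is a separate file, the main outcome needs 240 files. Adding the portal vein, which the hypothesis also names, gives 240 × 2 = 480 files, or 8 to 40 h.
- All four vessels as separate files: 240 × 4 = 960 files, or 16 to 80 h if done one by one.
- With more study days the scans rise to 10 × 8 × 4 = 320 for four days and 10 × 8 × 5 = 400 for five.

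**The case against.** The strongest reply is that the point rests on silence. The single-blind label does not say who is masked, and it could be the reader. Harm needs three conditions together: the reader knows the intervention, a person makes judgements on outlines or exclusions, and those judgements differ by intervention. The documents establish none of them. Flow is a calculated quantity, not a symptom score, so the room for judgement may be small. On this view a request to clarify who is masked would be enough.

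The premises are fair, and they are why no size of bias is claimed. They do not point to any text that masks the reading, however, and a calculated flow is only as objective as its outlines and exclusions. If the reader is already masked, one sentence settles the matter.

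Two further objections stand in part. The cost is softer than a single figure suggests: file structure, study days and minutes per file are all assumed, and 240 scans is a minimum. This affects the hours, not the case for masking. Coding also protects imperfectly. If a session's scans stay together, a reader who sees flow values may guess the intervention from the change over time, and slice placement and repeat scans at acquisition are not covered. Coding still removes direct knowledge of the intervention.

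The absence of a baseline adjustment is a separate matter of model specification. It is relevant here only because it determines which reading errors would cancel.

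**Conclusion.** The concern holds. As written, the plan allows the main outcome of a trial with a directional hypothesis to be derived with knowledge of the intervention. Neither the pairing nor the comparison after steady state would remove a reading difference that follows the intervention.

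The size is unknown and no bias is shown to have occurred. The consequence depends on a person influencing outlines or scan exclusion while aware of the intervention. The recommendation rests on two things: the gap concerns the main outcome, and closing it costs little relative to the trial. The change should be made; confidence is medium, because the reading procedure is not described.

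**What to change.** Before flow is calculated:

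1. Have an existing project member who does not read the images replace intervention and study day in the files with random codes, for all interventions.
2. Keep each session's serial scans together and randomise the order of sessions.
3. Have the existing reader outline vessels and decide any scan exclusion on the coded files only.
4. Lock the flow values before the code is broken.
5. State in the Design section that the image reader is masked, and who else is.

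If outlining is fully automatic, say so; masked decisions on scan exclusion are then enough. If masked reading is already the practice, write it down.

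No extra scan is needed, and no extra reader if flow is calculated from stored files, which the documents do not state. The cost is the coding time worked out above, with the main outcome first and the portal vein next if time is short. Administration of the infusions can stay single blind.

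### Does the mixed model treat repeat scans from one study day as independent replicates?

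*Combined protocol and SAP*

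**What the plan says.** The design is "Randomized, placebo controlled, crossover, single blind design in 10 healthy participants". Under Methods and outcomes the plan states: "The main outcome of the study is blood flow in superior mesenteric artery". Measurement is repeated within the day: "On each study day, 8 MRI scans are performed (-32 min to 60 min after start of infusion".

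The section Statistical analysis and graphs describes the model in one sentence: "The flow data is analyzed in Rs studio by a linear mixed model, that pairs the data". It adds that the analysis "compared the interventions after steady state of the infusion of GLP-2(3-33) antagonist". The primary comparison is between "Physiological dose of GLP-2 injection and highest dose of GLP-2-antagonist infusion + GLP-2 injection and placebo infusion". Results are to be tabulated "including mean and 95% confidence intervals".

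The plan does not give:
- the time at which steady state begins, or the number of scans after it;
- whether those scans are averaged or entered one by one;
- the random effects beyond whatever pairing implies, a period term, or a degrees-of-freedom method;
- the number of interventions (the background speaks only of "different doses of the GLP-2 receptor antagonist");
- a significance level.

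**The concern.** If each study day carries one intervention, the unit that receives an intervention is the participant-day, not the scan. In a crossover, pairing most naturally means a participant effect. A participant intercept removes differences between people. It does not remove the shift that all scans of one person on one day share, for example from hydration, posture or slice placement.

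If several scans per day are entered singly with nothing else in the model, that shared shift is treated as if it averaged out over scans. The standard error of the primary contrast is then too small and its 95% interval too narrow. The trial could conclude too readily that the antagonist blocks the GLP-2 effect. Because the rule is not written down, the choice could also be made after the data are seen. With only 10 participants, the number of scans treated as replicates matters.

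**Working it through.** The plan has no figure of its own to reproduce: it gives no significance level, power or sample-size derivation.

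**Inputs from the document.** n = 10 participants; 8 scans per study day from -32 to 60 min; main outcome superior mesenteric artery flow; one primary contrast between two interventions.

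**Inputs assumed.**
- m, scans per day in the window, 2 to 5. Even spacing gives a step of 92/7 = 13.1 min and scans at -32, -18.9, -5.7, 7.4, 20.6, 33.7, 46.9 and 60 min. Five of these follow the start of infusion. The plan does not state even spacing.
- ρ, the share of within-participant variance that lies between days, 0 to 50%.
- k, interventions in the model, 2 to 5.
- Two-sided 5% level, inferred from the 95% intervals.
- Scan errors independent within a day.

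**Formulae.** Set within-participant variance to 1, so the day variance is ρ and the scan variance is 1 − ρ.
- True variance factor of the contrast: λ = (1 − ρ) + mρ.
- The single-scan model's residual mixes (n−1)(k−1) degrees of freedom with mean λ and nk(m−1) with mean 1 − ρ.
- Residual df for single scans: nkm − n − k + 1. For day means: (n−1)(k−1).

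**One case in full: k = 4, m = 3, ρ = 0.2.**
- λ = 0.8 + 3 × 0.2 = 1.4.
- Single-scan df = 120 − 10 − 4 + 1 = 107, made up of 27 day-level and 80 scan-level. Day-mean df = 9 × 3 = 27.
- Expected single-scan residual = (27 × 1.4 + 80 × 0.8)/107 = 101.8/107 = 0.951, against the 1.4 needed.
- Rough check with the design effect: 1 + 2 × 0.2 = 1.4; 1.96/√1.4 = 1.66; two-sided tail 9.8%.

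**Simulated type I error, null true, 40,000 trials per setting, k = 4.**

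| m | ρ | Scans entered singly | One mean per day |
|---|---|---|---|
| 3 | 0 | 5.0% | 5.0% |
| 2 | 0.2 | 7.9% | 5.0% |
| 3 | 0.2 | 10.4% | 5.0% |
| 4 | 0.3 | 17.2% | 5.0% |
| 5 | 0.3 | 20.3% | 5.0% |

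The day-mean results scatter between 4.8% and 5.2% and are shown rounded. If only the two primary interventions are fitted (k = 2), single-scan error is 11.1% at m = 3, ρ = 0.2 and 32.6% at m = 5, ρ = 0.5. Over k = 2–5, m = 2–5 and ρ = 0.1–0.5 the range is about 6% to 33%. At ρ = 0 or m = 1 it is 5%.

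**Shared time course.** The table assumes flow does not drift over the window. A linear trend common to all days, spanning two within-participant SDs and left out of the model, enlarges the single-scan residual. The error then becomes about 3% at m = 3, ρ = 0.2 and 10.8% at m = 5, ρ = 0.3 (k = 4). The day-mean analysis stays near 5%. So even the direction of the single-scan error depends on something the documents do not give.

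**Interval width, day means relative to single scans.** With k = 4 the day-mean interval is 25% wider at m = 3, ρ = 0.2 and 60% wider at m = 5, ρ = 0.3; most of this is the single-scan shortfall. With ρ = 0 it is 2–5% wider for k = 3–5 and 8–11% wider for k = 2, before any period term.

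**The case for a change.** The best case for amending the plan is that the gap is real and sits in the primary analysis. No redaction explains it, and the arithmetic holds: two separate simulation methods agree on about 10–11% at three scans and a 20% day share. Even a 5% day share gives about 6.3% at k = 4, m = 3. Writing the rule would take a sentence and a line of code. It would also close off a choice made after the data are seen, in a study meant to establish a research tool.

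The omission and the figures stand. They do not show that the plan prescribes a wrong analysis. A linear mixed model can carry a day-within-participant term as easily as a participant term, and nothing in the plan excludes one. Pairing speaks to the participant; it does not say that scans enter singly. The times of steady state and of the GLP-2 injection are not given, so the window might hold one scan, and then there is no problem.

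Nor is there one obvious sentence to insert. Day means and a random day intercept are not interchangeable here. When there is no day-level variance, its estimate is zero in about half of trials, and the day-intercept test then rejects at 3–4% rather than 5%. Averaging every scan in the window would also mix flow before and after the injection if the injection falls inside it. These choices depend on details of the scan schedule that the analysts know and this short document does not set out.

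**Conclusion.** No change to the plan is called for. The document leaves out how the scans of one day are combined; it does not adopt a rule that gives a wrong result. The inflation arises only if two or more scans fall in the window, they enter singly, no day term or within-day covariance is fitted, and day-level variance exists. If all four hold, and there is no shared drift over the window, the primary test runs at about 6% to 33% against an inferred two-sided 5%, over the assumed grid of 2–5 interventions, 2–5 scans and a 10–50% day share. If any one fails, it does not exceed 5%.

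The stated method already accommodates a sound analysis: one value per participant-day, or a day effect within participant. An analyst used to crossover data with repeat measurements would be expected to choose one of these. When the results are reported, a reader should check that the degrees of freedom for the primary contrast reflect participant-days rather than scans.

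### The primary model names no same-day baseline flow term, although each study day's scans start before the infusion; adding one would probably narrow the interval at almost no cost

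*Combined protocol and SAP*

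**What the plan says.** Design gives a "Randomized, placebo controlled, crossover, single blind design in 10 healthy participants". Methods and outcomes states that "The main outcome of the study is blood flow in superior mesenteric artery", and sets the schedule: "On each study day, 8 MRI scans are performed (-32 min to 60 min after start of infusion". Read literally, at least one scan per day comes before the infusion. The split of the eight scans before and after that point is not stated.

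Statistical analysis and graphs says the flow data are analysed by a paired linear mixed model that "compared the interventions after steady state of the infusion of GLP-2(3-33) antagonist". The primary comparison is between "Physiological dose of GLP-2 injection and highest dose of GLP-2-antagonist infusion + GLP-2 injection and placebo infusion". No baseline covariate, change score or baseline time point is named.

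The only baseline section, Baseline information, is a descriptive table of "Age, Weight, Height, BMI, Hemoglobin, Leucocytes, Vitamin D, Fasting glucose, HbA1c, Sex, and Blood pressure". Flow is not in it.

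The number of conditions is not stated. Background asks "if different doses of the GLP-2 receptor antagonist (GLP-2(3-33)) can alter these flow changes". Several antagonist doses plus a placebo infusion make at least three conditions.

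**The concern.** In a crossover, pairing cancels whatever is constant about a participant. It does not cancel a participant's resting SMA flow being higher on one study day than on another. That variation goes straight into the error of the primary contrast. A scan taken the same day before the infusion measures part of it, and the plan appears to collect such scans without saying how they are used.

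Two things are at stake. One is precision: 10 participants leave little to spare, and the documents give no variance or power figure to show otherwise. The other is pre-specification: later values only, change from baseline and baseline as covariate can give different intervals for the main outcome, and the plan does not choose among them.

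**Working it through.** The plan gives no power, effect size or variance, so there is no figure of its own to reproduce. The question is how the width of the 95% confidence interval changes when a same-day baseline is added.

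**Inputs**
- n = 10 participants (Design).
- k = number of conditions in the model: 2 (primary pair only) or 3 (smallest number implied by Background). The documents do not state k.
- r = within-participant, day-level correlation of pre-infusion flow with flow after steady state. Not in the documents; assumed range 0, 0.3, 0.5, 0.7.
- One later value per participant and day, participant and condition effects, common residual variance and slope (assumptions).

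**Formulas**
- Residual degrees of freedom without baseline: df0 = (n − 1)(k − 1), which is 9 for k = 2 and 18 for k = 3. The baseline slope takes one, leaving 8 and 17.
- Variance factor, adjusted over unadjusted: (1 − r²)(1 + 1/(df0 − 2)). The second term is the price of estimating the slope: 8/7 for k = 2, 17/16 for k = 3.
- CI width ratio: √(variance factor) × t(df0 − 1)/t(df0). The t values are 2.306/2.262 for k = 2 and 2.110/2.101 for k = 3.
- Equivalent participants: 10 / variance factor.
- Change score, equal variances assumed: CI ratio √(2(1 − r)).

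**Example**, k = 3, r = 0.5: variance factor 0.75 × 17/16 = 0.797; √0.797 = 0.893; × 2.110/2.101 gives 0.90. Equivalent participants 10/0.797 = 12.5.

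| r | 0 | 0.3 | 0.5 | 0.7 |
|---|---|---|---|---|
| CI ratio, three conditions pooled | 1.035 | 0.99 | 0.90 | 0.74 |
| Equivalent participants | 9.4 | 10.3 | 12.5 | 18.5 |
| Power where unadjusted is 80% | 77–78% | 81% | 88% | 96–97% |
| CI ratio, two conditions only | 1.09 | 1.04 | 0.94 | 0.78 |
| Equivalent participants | 8.8 | 9.6 | 11.7 | 17.2 |
| Power where unadjusted is 80% | 74% | 78% | 85% | 95% |
| CI ratio, change score | 1.41 | 1.18 | 1.00 | 0.77 |

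The power rows come from simulation with a two-sided 5% test and the effect set to give 80% unadjusted power; both settings are illustrative.

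**Break-even.** Setting the CI ratio to 1 gives r = √(1 − [t(df0)/t(df0 − 1)]² / (1 + 1/(df0 − 2))). For k = 2: √(1 − (2.262/2.306)² × 7/8) = 0.40. For k = 3: √(1 − (2.101/2.110)² × 16/17) = 0.26. With four or five conditions it falls to about 0.2.

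**Check.** Simulating the fixed-effects version of the model gave mean CI ratios of 1.08, 1.03, 0.94 and 0.77 (k = 2) and 1.03, 0.99, 0.89 and 0.74 (k = 3), with adjusted coverage of 94.6% to 95.2%.

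**Which correlation counts.** A high raw correlation across people does not help. In simulation, a raw correlation of 0.80 with a within-participant correlation of 0 still left the standard error 7% larger after adjustment, because pairing had already removed the between-person part.

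**The case against.** The strongest reply is that nothing in the plan is wrong: the unadjusted contrast is valid, and the benefit rests on a correlation nobody has shown. Pairing has already taken out the stable part, so r could be modest. For the primary pair alone, any r below 0.40 means a small loss. This stands. It is why the point is an improvement rather than an error, and why the loss at low r is shown.

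The ratios are also averages over trials. In simulation the adjusted interval was the wider one in about 66% of single trials at r = 0.3 and 42% at r = 0.5 with two conditions, and in about half and a fifth with three. This stands too, and it favours pooling all conditions.

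The calculation leaves out period effects, which a crossover model may include. Adding them moves break-even to 0.43 (two conditions) and 0.28 (three), a minor shift. The equivalent-participant figures reflect variance only; counting the lost degree of freedom, 8.8 at r = 0 becomes about 8.4 (10/1.09²).

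The plan's wording could also fit a repeated-measures model of all eight scans. The text does not say so. With complete data, such a model would sharpen the later contrast only if it held pre-infusion means equal across conditions and modelled the day-level correlation, which is baseline adjustment by another route. The plan would still have to state it.

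Finally, pre-infusion scanning is inferred from the −32 minute start. If that time is counted from some other event, the sponsor must say which scans, if any, precede the infusion.

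**Conclusion.** The concern holds as a recommended improvement. The plan names no flow baseline in the primary model, and as written the data for one are collected on every study day. With all conditions in one model, the expected downside is an interval about 3.5% wider if r is 0; the upside is an interval about 10% narrower at r = 0.5 and 26% narrower at r = 0.7. With only the two primary conditions the trade is less favourable: 9% wider at r = 0, 6% narrower at r = 0.5, 22% narrower at r = 0.7.

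This rests on the literal reading of the scan times, on at least three conditions for the pooled figures, and on a common variance and slope. Because r is unknown, the gain is likely to be worth having but is not assured, and confidence is medium.

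**What to change.** State in Statistical analysis and graphs that one mixed model is fitted to all conditions, and that it includes that day's mean pre-infusion SMA flow in two parts: its deviation from the participant's own mean baseline, and that participant mean. The deviation does the work. In complete, balanced data the mean does not sharpen the within-participant contrast; it keeps between-person differences out of the deviation's slope.

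Name the scans that form the baseline, use only those taken before the infusion starts, and average them. Do not make a change score the primary form: it is worse than pooled adjustment throughout the range examined and gains nothing until r exceeds 0.5. Treat the portal vein, celiac trunk and hepatic artery in the same way, each with its own baseline.

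The cost is one or two sentences and no new scans. The deviation term uses one degree of freedom (18 to 17 with three conditions, 9 to 8 with two), and a little precision is lost if r turns out to be low.

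### The primary flow window is tied to antagonist steady state, not to the GLP-2 injection, has no stated clock time for saline days, and leaves the same-day earlier scans unused

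*Combined protocol and SAP*

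**What the plan says.** Under Statistical analysis and graphs, the flow data go into a linear mixed model that "compared the interventions after steady state of the infusion of GLP-2(3-33) antagonist". The primary contrast is given as "Physiological dose of GLP-2 injection and highest dose of GLP-2-antagonist infusion + GLP-2 injection and placebo infusion". The wording is loose; the most natural reading is GLP-2 injection with the highest antagonist dose against GLP-2 injection with placebo infusion.

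Under Methods and outcomes, flow is measured "during the infusion of either saline or GLP-2(3-33) receptor antagonist and injection of GLP-2", and on each study day "8 MRI scans are performed (-32 min to 60 min after start of infusion) and four blood samples are taken". The outcome is stated as "The main outcome of the study is blood flow in superior mesenteric artery", without a time point, summary measure or baseline adjustment. On the samples, the plan says: "The blood samples collected are kept for analysis of GLP-2(1-33), GLP(3-33) and markers of bone metabolism".

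The hypothesis in the opening section is that the antagonist blocks the flow effects of GLP-2. The documents give no injection time, no minute or criterion for steady state, no list of individual scan times and no blood sampling times.

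**The concern.** The study asks whether the antagonist blocks the response to an injection, but the window that supplies the data is defined by the state of an infusion. Three things follow.

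- **Window and question are not linked in the text.** Any scan after steady state but before the injection would qualify, although it carries no response to block.
- **The cut-off is not fixed.** Saline days have no antagonist steady state of their own, so a time has to be carried over to them, and none is written down. While it is unwritten, it could be settled after the flow curves or the stored-sample results are seen.
- **Same-day earlier scans are not used.** Scans run from -32 min, but the stated comparison is post-only. Day-to-day variation in flow within a participant is then left in the contrast. If the antagonist has any flow effect of its own, nothing in the comparison helps to tell it from blocking.

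This sentence determines the data behind the main result of a study with 10 participants.

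**Working it through.** **Is there a figure to reproduce?** No. The plan states 10 participants without effect size, SD, alpha or power. Everything below is illustration, assuming a two-sided 5% level and a paired comparison.

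**1. Timeline.** The scans span 60 + 32 = 92 min. With even spacing (an assumption), the interval is 92/7 = 13.1 min, which puts 3 scans before and 5 after the stated zero. If zero is the start of infusion, as the text reads literally, the negative-time scans are pre-infusion. Where the injection falls is not stated.

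**2. Starting point.** Power = P(|T| > 2.262), where T is noncentral t with 9 df and noncentrality d√10. Power of 80% needs d = 0.996 (noncentrality 3.150).

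**3. Dilution.** If a fraction f of the scans in an averaged window precedes the injection and carries no effect, d becomes 0.996 × (1 − f). With the SD held fixed:

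| f | d | power |
|---|---|---|
| 1/6 | 0.830 | 64.8% |
| 1/5 | 0.797 | 61.3% |
| 1/4 | 0.747 | 55.9% |
| 1/3 | 0.664 | 46.6% |
| 2/5 | 0.598 | 39.3% |

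If the SD instead depends on the number of scans averaged, with correlation ρ of 0.8 to 0.3 between the paired differences, a 5-scan window gives 62% to 65% at 1/5 and 40% to 46% at 2/5. The fractions are assumed; the documents do not show that any such scan exists.

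**4. Cut-off chosen after seeing data.** Simulation of 40,000 null trials: n = 10, five scans, compound-symmetric correlation 0.3 to 0.8, every window running to the last scan, and the trial counted as positive if any candidate start gives p < 0.05. Type I error is about 6% to 8% with 3 candidate starts and about 8% to 12% with 5. The top of the range needs correlation 0.3 and five starts, one of which leaves a single-scan window.

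**5. How to use the earlier scans.** Take 4 post-injection scans and 1 pre-injection scan, scaled so that 5 post-injection scans would give 80% power. The variance of a mean of k paired differences is v(k) = (1 + (k − 1)ρ)/k. At ρ = 0.3, v(5) = 0.44 and v(4) = 0.475.

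- Post-only: variance 0.475; d = 0.996 × √(0.44/0.475) = 0.959; power about 77%.
- Change score: variance 0.475 + 1 − 2(0.3) = 0.875; d = 0.706; power about 51%.
- Baseline covariate: variance 0.475 − 0.3² = 0.385; d = 1.065; power about 85%, ignoring the lost degree of freedom.

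At ρ = 0.5, v(5) = 0.60 and v(4) = 0.625. The change score has variance 0.625 + 1 − 1 = 0.625, so it equals post-only at about 78%. The covariate has variance 0.625 − 0.25 = 0.375, d = 1.260 and power about 94%. The covariate is therefore the safer choice when the correlation is unknown.

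**6. The antagonist's own effect.** Suppose the antagonist alone shifts flow by a constant amount of −30% to +30% of the blocking effect (assumed). An all-post-injection, unadjusted contrast then estimates 70% to 130% of the blocking effect. A pre-infusion baseline carries no information on this shift. An on-infusion, pre-injection baseline with slope b removes the fraction b of it: at b = 0.3 and a +30% shift, 100% + 30% × (1 − 0.3) = 121%. Adjustment helps but does not finish the job, so a separate contrast on those scans is also needed.

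**The case against.** The strongest reply is that steady state here may simply mean a preset number of minutes after the infusion starts. Scan times are counted from that start on each study day, and saline days also have an infusion, so one clock time would transfer directly. If the injection is given at or after that time and only later scans are used, there is neither dilution nor a post hoc choice. The plan also names a mixed model, not an average, and a model with time terms need not dilute anything.

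Much of this stands. A reader might infer that the rule cannot be applied to saline days at all, that steady state can only be judged afterwards, or that the primary contrast is in fact diluted. The documents support none of these. They do not show scans between steady state and injection, they do not say that the cut-off will be set late, and they do not suggest a flow effect of the antagonist on its own. The interventions are not fully listed, so a day with antagonist but no GLP-2 cannot be ruled out either.

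The reply does not supply the missing rule. The clock time, the injection time and any time structure in the model are all unstated. Even on the favourable reading, the comparison is anchored to the infusion and makes no stated use of the same-day earlier scans.

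**Conclusion.** The concern holds in a limited form. The primary window is defined by the infusion and not by the injection under study, has no stated time that carries over to saline days, and leaves same-day earlier scans out of the comparison. That is more than a missing detail, because an injection-anchored comparison with same-day baseline would be a different and better-targeted analysis of data already being collected.

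The harm is conditional and neither its size nor its direction can be derived from the documents. If one scan in five preceded the injection, power would fall from an assumed 80% to about 61%; if two in five, to about 39%, both with the SD held fixed. If the window start were picked for the best result, type I error would be about 6% to 12%. These figures rest on a two-sided 5% test, assumed scan splits and assumed correlations. They illustrate what the wording permits and do not describe what will happen.

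**What to change.** Before analysis, and without reference to the flow results:

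1. Define the primary window as a list of post-injection scans, at the same nominal times from GLP-2 injection on every study day, including saline days.
2. Enter the same-day mean of the pre-injection scans as a baseline covariate in the linear mixed model, in preference to a simple change score.
3. State whether those baseline scans are pre-infusion or on-infusion. Only on-infusion, pre-injection scans can help to separate the antagonist's own effect from blocking. If such scans exist, report antagonist against saline on them as a secondary contrast.
4. Reconcile the statements on infusion, injection and scan times so that each scan can be placed relative to all three, and say what zero means in the range from -32 to 60 min.

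The cost is wording. Any pre-injection scans leave the primary average and one degree of freedom goes to the covariate. At a correlation of 0.3 in the illustration, averaging four scans instead of five takes power from 80% to about 77%, and the covariate more than recovers that. No scans or visits are added.
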